5. PROTOCOL SYNOPSIS

Protocol Title	Intra-Arterial Dexamethasone for the Alleviation of Pain and Postembolization Syndrome Following Uterine Artery Embolization (UFE).
Targeted Patient Population	Women aged 20-50 years with symptomatic uterine fibroids.
Study Design	Randomized double blind placebo control trial.
Treatment Schema	Direct intra-arterial dexamethasone delivery to the uterine arteries at the time of embolization for minimizing the post embolization pain, narcotic use, nausea and vomiting and hospital stay.
Duration of Treatment	Intra-arterial dexamethasone will be administered during standard UFE procedure protocol
Follow-up Required Post-Treatment	
To evaluate specific aim 1: Pain will be assessed using 11 point visual analog scale as below:
 
The visual analog pain score will be documented as follows:
 
 ○ Time 0 Immediately prior to the procedure ○ 1 hour intervals for the first 3 hours ○ 3 hour intervals for the next 9 hours ○ 6 hour intervals for the next 12 hours ○ Daily, for the next 3 days ○ Once at day 7 
First 3 of those surveys will be done in the recovery area The amount of narcotic use from PCA pump will also be recorded.
 
To evaluate specific aim 2: Post embolization syndrome will be assessed as reporting of nausea, vomiting and pain scores, that will be assessed at least twice during the day of the procedure and then daily for the next 3 days and then at 7 days. We will utilize our previously mentioned UFE Pain and PED Survey.
 
To evaluate specific aim 3: Symptom relief and patient satisfaction will be measured through the completion of a UFE health-related quality of life (QOL) survey, UFE QOL Survey, prior to the procedure and then at 1 month and 3 month after procedure.

	Uterine fibroid volume change will be measured by comparing the pre procedure and 3 month post procedure MRI using volumetric software.
Objectives	
SA1: Assess the efficacy of intra-arterially delivered dexamethasone for the alleviation of post-procedural pain following UFE.
 
SA2: Assess the efficacy of intra-arterially delivered dexamethasone for the alleviation of post embolization syndrome in UFE.
 
SA3: Compare the fibroid volume change, symptom relief and patient satisfaction from UFE between patients who received steroids versus those who did not.

Expected Number of Patients	Approximately 42 patients

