Expected Number of Centers	University of Miami Health Towers University of Miami Hospital and Clinics Lennar Foundation Medical center
Expected Duration of the Study	2 years
Inclusion Criteria	Women aged 20-50 years undergoing UFE for symptomatic fibroids
Exclusion Criteria	Women aged <20 or >50 years, those pregnant or actively attempting to conceive, those deemed mentally impaired to make their own medical decisions, previous documented allergy to dexamethasone, those currently taking daily steroids for any reason, those with diabetes or deemed to be pre-diabetic, those with contraindications for angiography, and prisoners.

6. Objectives*

Uterine fibroid embolization (UFE) is a proven minimally invasive and uterine sparing technique for the treatment of symptomatic fibroids. The procedure is associated with significant post procedure cramping along with nausea and vomiting which require a high dose of non-steroidal anti-inflammatory medications (NSAID) and IV patient controlled analgesia with opioids. This can sometimes translate to increased length of hospital stay, and the possibility of readmission [1, 2]. Recently, a study by Kim, et. al., has shown that the use of preprocedural oral dexamethasone decreases these clinically apparent side effects seen following UFE [3].

In this proposed randomized double blind placebo control trial, we propose the use of intra-arterial dexamethasone, delivered directly to the uterine arteries at the time of embolization for the treatment of post-UFE pain and post-embolization syndrome. We hypothesize that the anti-inflammatory effects from the high dose of steroids delivered directly to the uterus, bypassing the first pass metabolism and systemic dilution, will lead to lower pain scores, decline in narcotic use, lower incidence of nausea and vomiting and shorter hospital stay.

The specific aims of the study are:

1. To assess the efficacy of intra-arterially delivered dexamethasone for the alleviation of post-procedural pain following UFE.
2. To assess the efficacy of intra-arterially delivered dexamethasone for the alleviation of post embolization syndrome in UFE.
3. To compare the fibroid volume change, symptom relief and patient satisfaction from UFE between patients who received steroids versus those who did not.

7. Background*

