All eligible women, in whom UFE is not inherently contraindicated, will be screened based on the following Inclusion/Exclusion criteria during their initial clinic appointment to discuss UFE. This will consist of a standardized questionnaire administered with participation from the primary physician and utilize standardized teach-back techniques to ensure patient understanding [24].

Inclusion: Women aged 20-50 years, undergoing UFE for symptomatic fibroids.

Exclusion: Women aged <20 or >50 years, those pregnant or actively attempting to conceive, those deemed mentally impaired to make their own medical decisions, previous documented allergy to dexamethasone, those currently taking daily steroids for any reason, those with diabetes or deemed to be pre-diabetic, those with contraindications for angiography, and prisoners.

9. Number of Subjects*

The power calculation is primarily based on the paper from Kim et al, which evaluated the effect of IV dexamethasone for treatment of post UFE pain and PES [3]. Based on this study, the mean Visual Analogue Scale for the Dexamethasone group was 2.89 (SD 1.09) compared to 3.91 (SD 2) for controls. However, in contrast to the reference study, the proposed study utilizes intraarterial drug delivery directly into uterus instead of IV route drug, which results in higher concentration in the uterus [25-27]. For a low flow organ such as uterus, intraarterial delivery of a low clearance drug such as dexamethasone will result in a regional advantage of 10-25 times compared to IV or oral delivery as shown by Daemen et al. [25]. Given the significantly enhanced organ drug concentration in the uterus, an increase in effect size of at least 50% is expected with intraarterial drug administration compared to IV route. To detect a difference 50% larger between control group and intervention group, using a two-sample t test with significance level of 0.05, sample size of 21 per group will provide us with 86% statistical power to detect such an effect size.

10. Study-Wide Recruitment Methods*

As with the discussion of Inclusion/Exclusion criteria, participants will be introduced to the study at the time of their initial clinical visit (referred for UFE through typical channels), and once they have already met criteria for undergoing a UFE for symptomatic fibroids. The patients will not be actively recruited for this study, per say, but will be offered admission to it providing they meet criteria.

11. Study Timelines*

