All patients will have a routine 2 week post-procedural phone call to review their symptoms, 1 month clinic visit and then 3 month clinic visit after MRI imaging.

All data collected from the Surveys will be stored and analyzed as described elsewhere in this proposal. Again, we expect that this study will reach its recruitment goal and Primary Endpoint in approximately 2 years.

To evaluate specific aim 1:

Pain will be assessed using 11 point visual analog scale as below:

The visual analog pain score will be documented as follows:

- Time 0 Immediately prior to the procedure
- 1 hour intervals for the first 3 hours
- 3 hour intervals for the next 9 hours
- 6 hour intervals for the next 12 hours
- Daily, for the next 3 days
- Once at day 7

First 3 of those surveys will be done in the recovery area. The amount of narcotic use from PCA pump will also be recorded.

To evaluate specific aim 2:

Post embolization syndrome will be assessed as reporting of nausea, vomiting and pain scores, that will be assessed at least twice during the day of the procedure and then daily for the next 3 days and then at 7 days. We will utilize our previously mentioned UFE Pain and PED Survey.

To evaluate specific aim 3:

Symptom relief, patient satisfaction and fibroid volume change will be measured through the completion of a UFE health-related quality of life (QOL) survey, UFE QOL Survey, prior to the procedure and then at 1 month and 3 month after procedure.

Uterine volume will be compared from the pre-procedure and 3 month post procedure MRI using volumetric software.

14. Data and Specimen Banking*

No specimen will be collected or stored. Data will be kept in password protected, HIPAA compliant University approved Box folder, accessible only to investigators.

15. Data Management*

All data will be stored, accessed, and analyzed utilizing server and computer workstations previously approved as HIPAA compliant. Data will be kept in password protected, HIPAA compliant University approved Box folder, accessible only to investigators. Anonymized data will include age, pre and post MRI imaging, UFE Pain & PES Survey, narcotic use, vital signs, subjective reports of nausea, vomiting, daily dietary intake, bowel movements, length of hospital stay, readmission rate, and days to return to baseline.

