A single computer system managed by the Pharmacology Research Coordinator, [name], will be maintained to ensure blinding of the cohorts. Collected data will be analyzed by [name], and done so prior to unblinding.

16. Provisions to Monitor the Data to Ensure the Safety of Subjects*

All data will be analyzed as it arrives and on a rolling basis by the primary physicians and researchers directly involved in this study, to ensure that the clinical findings and participant reported responses to the Pain & UFE Survey are not deviating in a way that could lead to undue harm.

As stated previously, all participants will be admitted to the hospital for observation for the first 24 hours and discharged with 2-week clinical follow-up in place and the contact information of a research team member. All participants will be contacted daily for the first 3 days, then at 7 and 14 days following the procedure. Any adverse effects of safety issues would be discovered in this follow up.

At 6 months we will analyze the interim data for any difference in the efficacy of treatment between the groups. All data will be analyzed using IBM SPSS software. We will use Student's T test for analysis of continuous variables, Chi square test for categorical variables with significance level set at two tailed p value of <0.05.

Although we expect that this trial exposes the participants to minimal risk, we consider the following statistically-significant differences between the two arms to be grounds for immediate trial termination: excessive abnormal uterine bleeding, infection, and sepsis.

17. Withdrawal of Subjects*

Subjects will be immediately withdrawn if it is deemed at any time prior to the procedure date that they fall into any of the previously outlined Exclusion criteria, suffer an intra-procedural adverse reaction to the use of dexamethasone, or willingly choose to leave the trial at any time.

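### Aim 3 compares fibroid volume change between arms without defining the scale of change or settling which structure is measured; a log volume ratio with baseline adjustment would fix the scale at no extra data cost

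*Combined protocol and SAP*

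**What the plan says.** Specific aim 3 (Section 6) is "To compare the fibroid volume change, symptom relief and patient satisfaction from UFE between patients who received steroids versus those who did not". The synopsis (Section 5) gives the measurement: "Uterine fibroid volume change will be measured by comparing the pre procedure and 3 month post procedure MRI using volumetric software". Section 13 schedules a 3-month MRI for every patient to gauge treatment response. Its paragraph on aim 3 then names a different structure: "Uterine volume will be compared from the pre-procedure and 3 month post procedure MRI using volumetric software". The same paragraph also lists fibroid volume change among the things captured by the quality-of-life survey.

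The only analysis rule is in Section 16, beside the 6-month interim look: "We will use Student's T test for analysis of continuous variables", with "significance level set at two tailed p value of <0.05". No section names a scale for the change, a transformation, a baseline covariate or an interval estimate. No mean, SD, expected difference or power is given for volume. Section 9 powers the trial on pain only, and Section 12 does not list volume among the secondary endpoints.

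**The concern.** Aim 3 is where the trial can show whether the steroid alters fibroid shrinkage. Eligibility sets no limit on fibroid size, and Section 12 itself treats fibroid number and volume as differing between patients. If shrinkage is roughly proportional to starting size, a change in mL largely records how big the fibroids were at entry, and an unadjusted t test carries that variation as noise.

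Two things are at stake. With the scale undefined, mL, percent or ratio could be chosen after the data are seen. And if mL is used with 21 per arm and no planned interval, a non-significant result could be read as no effect on treatment response when the comparison had little chance of showing one.

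**Working it through.** **The plan's own figure.** Section 9 states 86% power, for pain: "the mean Visual Analogue Scale for the Dexamethasone group was 2.89 (SD 1.09) compared to 3.91 (SD 2) for controls", with the effect enlarged by 50%.
- Difference: 1.5 × (3.91 − 2.89) = 1.53.
- Pooled SD: √[(1.09² + 2²)/2] = 1.611, so d = 1.53/1.611 = 0.950.
- With 21 per arm and two-sided 0.05, power is 86.8% by normal approximation and 85.2% by noncentral t. The stated 86% reproduces.

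There is no volume figure to reproduce. From here, 21 per arm and two-sided 0.05 come from the plan; every volume input is an assumption.

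**Why the scale matters.** Let V be starting volume with coefficient of variation CV, and R the fraction remaining at 3 months, independent of V. Let m and s² be the mean and variance of 1 − R. In units of mean starting volume, the mL change has mean m and variance s²(1 + CV²) + m²CV². The last term is variation in starting size alone. Percent change has variance s².

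**Worked example.** CV 1.0, log-normal R with log SD 0.35, median shrinkage 40% v 55%.
- Control: mean R = 0.60 × exp(0.35²/2) = 0.638; m = 0.362; s² = 0.638² × [exp(0.35²) − 1] = 0.0530; mL variance = 2 × 0.0530 + 0.131 = 0.237.
- Steroid: mean R = 0.478; m = 0.522; s² = 0.0298; mL variance = 2 × 0.0298 + 0.272 = 0.332.
- mL: d = 0.159/√0.284 = 0.30; d√(21/2) = 0.97; power about 16% (simulated 18.5%).
- Percent: d = 0.159/√0.0414 = 0.78; d√(21/2) = 2.54; power about 72% (simulated 71.2%).
- Log ratio: d = ln(0.60/0.45)/0.35 = 0.82; d√(21/2) = 2.66; power about 76% (simulated 73.5%; 72.3% with ANCOVA on log baseline).
- ANCOVA of mL change on baseline: simulated 49.6%.

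**Range.** The effect is 0.9 SD on the log scale with SD of log ratio 0.3–0.4. That is 40% shrinkage v 1 − 0.60·exp(−0.27) = 54% to 1 − 0.60·exp(−0.36) = 58%. CV = √[exp(log SD²) − 1]. Simulated power:

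| Baseline log SD | CV | Change in mL | Log ratio |
|---|---|---|---|
| 0.3 | 0.31 | 56–61% | about 81% |
| 0.6 | 0.66 | 27–35% | about 81% |
| 0.83 | 1.0 | 17–23% | about 81% |
| 1.2 | 1.8 | 9–13% | about 81% |

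The last column is constant because the effect is set on that scale. Adding log baseline costs about 1 point, giving about 80%. Percent change has about 79%. Simulation error is up to about 1 point.

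**Opposite direction.** With the same 0.9 SD reversed, steroid shrinkage is 1 − 0.60·exp(0.27) = 21% to 1 − 0.60·exp(0.36) = 14%. Power for mL change is 20–59% at log SD 0.6–1.2 and up to 73% at 0.3.

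**Type I error.** With no true difference, all methods reject in about 3 to 6% of trials.

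**Baseline adjustment.** When shrinkage depends on size (log-scale slope ±0.2), adjusting the log ratio raises power from 69.4% to 72.6% and from 69.9% to 73.2% at CV 0.6, and from 65.0% to 72.5% and from 64.8% to 71.9% at CV 1.0. Over log SD 0.3–1.2 the gain is 0 to 21 points.

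**Modest effects.** For 40% v 50% shrinkage with SD of log ratio 0.35, log-ratio power is about 37%. The 95% half-width on the log scale is about 2.02 × 0.35 × √(2/21) = 0.22, a factor of 1.24 either way, while the effect is ln(0.60/0.50) = 0.18.

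**The case against.** A reader might infer that the plan specifies a t test on mL, that a few large uteri dominate its variance, and that a log ratio would give several times the power. The documents support none of these as fact.
- The scale is undefined. A t test on percent change fits the text equally well, and the log-ratio ANCOVA has only 0.99 to 1.31 times its power.
- No volume distribution is given, so skew and proportional shrinkage are assumptions. The log-normal, multiplicative model used above favours the log ratio.
- The multiple depends on the inputs. Across the scenarios run, the log-ratio ANCOVA had 1.2 to 11.8 times the power of the mL test, but only 1.2 to 1.8 times at CV 0.3. It is also smaller when the steroid impairs shrinkage, a direction the hypotheses in Section 6 do not rule out.
- Nearly all of the gain comes from the proportional scale rather than from baseline adjustment.

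Volume is also a lower-tier outcome with no power claimed, and the mL test does not inflate type I error.

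All of this stands, and it limits the size of the point. It does not remove the omission: under every reading, the structure, the scale and the use of the baseline MRI are left unspecified.

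**Conclusion.** The point holds as a gap in specification with a conditional cost in power. The plan does not define the scale of volume change, names only an unadjusted t test, and alternates between fibroid and uterine volume. If mL is used, and if starting volumes are skewed with roughly proportional shrinkage, power falls from about 80% to about 9–35% at baseline log SD 0.6–1.2, or to 56–61% at 0.3. With the effect reversed, mL power is about 20–73%. If percent change was intended, little power is lost, but the plan should say so. Baseline adjustment adds nothing when shrinkage is unrelated to size and protects power when it is related. No error in type I control is shown. The change is worth making because it needs no new data.

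**What to change.** In Section 13 (aim 3) and Section 16:
1. Reconcile fibroid with uterine volume and name one structure throughout. Remove volume from the list of things measured by the quality-of-life survey.
2. Define the outcome as log(3-month volume / pre-procedure volume).
3. Compare arms by ANCOVA on arm and log pre-procedure volume.
4. Report the exponentiated arm effect with a 95% CI as the between-arm ratio of geometric mean volume ratios, that is, of the fraction of volume remaining. It is not a ratio of percent shrinkage: for 40% v 54% shrinkage the model gives 0.46/0.60 = 0.77, whereas the ratio of shrinkages is 54/40 = 1.35.
5. Prespecify how missing 3-month MRIs and zero volumes (which have no logarithm) are handled.
6. State that a non-significant result will be interpreted from the interval.

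The cost is wording only. The same MRIs and software are used, and the adjustment costs about 1 point of power if shrinkage turns out to be unrelated to size.

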We intend to start the study by 10/2020 and to complete recruitment in 2 years, completing in 10/2022

Unless a patient chooses to opt-out of the study, a participant's duration will be limited to a total of 15 days beyond the procedural date. This will include periodic assessments of a subjective and objective measure, as outlined later in this proposal.

[figure not shown]
Enrollment and data analysis will be conducted on a rolling basis and deemed complete upon either meeting the primary endpoints (detailed below) or in the face of severe adverse events related to the procedural modification (detailed below).

12. Study Endpoints*

Primary end point of this study is post procedure pain. As such, pain is measured using a modified Visual Analogue Score (VAS), a numerical rating system that each patient assigns to their level of pain, at a particular time [28]. The study endpoints will include qualitative and quantitative collection of data. Pain following UFE is subjective and unique to each patient and can be based on the location, number of the fibroid(s) and the volume of fibroid(s). A modified VAS, termed *UFE Pain and PES Survey*, will be utilized to assess pain prior to and following the procedure (Pre, immediately after the procedure, and periodically for the next 13 days, as described below). Our primary endpoint will be a 3-point decrease in the UFE Pain & PES score between test and controls.

Secondary endpoints will include assessment of PES based on the measurement of nausea, vomiting, subjective fevers or chills, subjective data obtained from return to work times and readmission rates. This will be assessed in part using our *UFE Pain and PES Survey*, which includes a previously validated numerical scoring system

(0-3) to categorize nausea and vomiting, as well as a “Yes” or “No” scoring system to evaluate subjective fevers or chills.

13. Procedures Involved*

The Uterine Artery Embolization procedure with the proposed intervention is detailed below, italicized section denotes the interventions which are additions to the standard of care. The procedure is separated into Pre-Procedure Assessment and Imaging, Uterine Artery Embolization Procedure, and Post-Procedure Assessment and Imaging.

Pre-Procedure Assessment and Imaging:

- All accepted UFE study participants will be initially assessed using the attached UFE Pain & PES Survey to ascertain their current baseline pain.

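### Sections 11 and 12, read literally, end enrolment on an observed 3-point difference, and the 6-month efficacy test in Section 16 has no boundary or stated consequence

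*Combined protocol and SAP*

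**What the plan says.** **Completion rule.** Section 11: "Enrollment and data analysis will be conducted on a rolling basis and deemed complete upon either meeting the primary endpoints". The alternative trigger in the same sentence is severe adverse events. The sentence refers forward for the definition of the endpoint.

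**Primary endpoint.** Section 12 gives two versions: first "Primary end point of this study is post procedure pain", then "Our primary endpoint will be a 3-point decrease in the UFE Pain & PES score between test and controls". Neither carries a time point, a test, a minimum sample or a number of looks.

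**6-month look.** Section 16: "At 6 months we will analyze the interim data for any difference in the efficacy of treatment between the groups". The tests are Student's t and chi-square, "with significance level set at two tailed p value of <0.05". That one level covers everything; nothing is set aside for the interim look, and no action follows from its result. The only statistical termination rule in Section 16 makes "statistically-significant differences between the two arms to be grounds for immediate trial termination", and it is limited to three safety outcomes.

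**Planned size.** Section 9 powers a single two-sample t test at 0.05 with 21 per group. The Synopsis expects "Approximately 42 patients", and Section 11 also says "We intend to start the study by 10/2020 and to complete recruitment in 2 years, completing in 10/2022". Section 13 expects the recruitment goal and the primary endpoint to arrive together at about two years. Section 28 describes 21 per arm as the minimum for adequate power. None of these statements is tied to the completion rule.

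**The concern.** The plan does not settle two things that decide how the primary p-value should be read: when enrolment ends, and which test decides success.

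If enrolment may end as soon as the running difference reaches 3 points, it ends at a high point of a noisy series, probably with few patients. The reported effect would then overstate the true one. If the 6-month test may also be declared positive, the trial has two chances at 0.05, and the 5% in Sections 9 and 16 no longer describes the overall false-positive risk.

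**Working it through.** **Inputs.** Section 9: means 2.89 (SD 1.09) and 3.91 (SD 2), an effect 50% larger, 21 per group, 0.05. Section 11: 24 months of recruitment. Section 12: 3 points. Section 16: a look at 6 months, two-sided 0.05.

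**1. The plan's own power figure.**
- Difference: 3.91 − 2.89 = 1.02; × 1.5 = 1.53.
- Pooled SD: √((1.09² + 2²)/2) = 1.61. Standardised effect: 1.53/1.61 = 0.95.
- Power at 21 per arm: 85.2% (noncentral t) or 86.8% (normal approximation). The stated 86% is reproduced. It is a single-look calculation.

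**2. Two tests at 0.05.** The plan gives no sample size for the look. I assume even accrual and count 6 months from study start: 6/24 = 0.25, and 0.25 × 21 ≈ 5 per arm.
- Normal theory: 1 − P(|Z₁| < 1.96, |Z₂| < 1.96) with correlation √0.25 = 0.5 gives 9.1%.
- Simulated pooled t tests at 5 and then 21 per arm, either counting:

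| What counts at 6 months | Equal SDs (1.61) | Cited SDs (1.09 and 2) |
|---|---|---|
| Significance in either direction | 9.2% | 10.0% |
| Only a result favouring dexamethasone | 7.1% | 7.6% |
| Nothing (final test alone) | 5.0% | 5.2% |

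- With equal SDs, a look at 8 down to 3 per arm gives 8.8% to 9.4%.
- At 5 per arm the look has 26% power at a true difference of 1.53. Significance needs an observed 2.306 × 1.61 × √(2/5) = 2.35 points. Significant results average about 2.6, or 1.7 times 1.53.

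**3. The 3-point stop when the true difference is 1.53.** I assume that the Section 12 score behaves like the reference study's pain VAS, with SD 1.61.
- At 21 per arm: SE = 1.61 × √(2/21) = 0.497; (3 − 1.53)/0.497 = 2.96; probability about 0.15%.
- At 5 per arm: SE = 1.61 × √(2/5) = 1.02; (3 − 1.53)/1.02 = 1.44; probability about 7.5% at that one look.
- Checked at every size from 5 per arm on (simulated): triggered in 10.7% of trials, at 5.9 per arm on average, with mean estimate 3.36; 3.36/1.53 = 2.2. Checked from 3 per arm, it triggers in 19%.
- Checked only after each complete block of 8 (an assumed schedule): 11.4%, at 4.7 per arm on average, with mean estimate 3.49.

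**4. The 3-point stop when there is no effect.** Stop plus final test, with the 6-month look not counting:
- SD 1.61, from 5 per arm: 5.1%, so about 0.1 point is added.
- SD 2 in both arms: 5.8% from 5 per arm and 8.6% from 3 per arm.

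The added type I error is therefore small only if the SD is near 1.61 and the rule is not applied to very few patients. The documents guarantee neither.

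**The case against.** **The text points to full recruitment.** The Synopsis and Sections 9, 11, 13 and 28 all give 42 patients, 21 per arm or two years, and Section 13 couples the recruitment goal with the primary endpoint. The Section 11 clause may be loose wording for completing the study. That is plausible, and a reader should not infer that the trial was meant to stop early or did so. But these statements are targets and expectations, and the completion clause refers to none of them.

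**The protocol never says the 6-month test counts.** This stands. The look sits under safety monitoring and has no success claim attached. A reader might infer that the design has a 9–10% error rate; the documents do not support that as an unconditional statement. The 10% end also requires the arms to have different SDs when the drug does nothing. With a common SD the figure is 9.2%, and 7.1% if only a favourable result counts.

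**The score may not be a pain VAS.** This also stands. The survey named in Section 12 includes nausea, vomiting and fever items, so SD 1.61 is borrowed, and steps 3 and 4 depend on it.

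**Blinding.** A reader might infer that nobody is assigned to run by-arm comparisons, or that blinding is broken. Section 15 does assign an analyst (the name is removed) and places analysis before unblinding. Comparing coded groups would fit that. What remains is a clarification.

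**Conclusion.** The concern holds in conditional form. Sections 11 and 12 allow a literal reading that conflicts with the fixed 21 per arm in Section 9, and Section 16 leaves the role of the 6-month test open.

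- **Type I error:** about 9% if the 6-month test can count as success, within a range of 7% to 10% set by which direction counts and whether the SDs differ. It is 5% if the look has no consequence. This rests on even accrual and about 5 per arm at the look.
- **3-point stop:** the main harm is exaggeration. It would affect about 11% of trials if checked from 5 per arm and 19% from 3 per arm. The mean estimate is about 3.4 in the first case. This rests on SD 1.61 and a true difference of 1.53.
- It would be too strong to say that the 3-point rule never matters for type I error: with SD 2 in both arms it can.

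**What to change.** 1. **Section 11.** Delete meeting the primary endpoints as a reason to end enrolment. State that the planned 42 are enrolled unless the trial ends on the safety grounds already in the protocol.
2. **Section 12.** State that the 3-point difference is not a stopping rule and that success is judged by the single final test.
3. **Section 16.** Either drop the 6-month efficacy comparison or keep it with a strict boundary. One option is Haybittle-Peto: p < 0.001 at 6 months and 0.049 at the end, for an overall error of about 5%. If the look has already been taken, report it and whether it affected enrolment. A 10/2020 start would put it at about 04/2021, before the 09/12/2023 revision listed in Section 4.
4. **Sections 15 and 16 (secondary clarification).** Have the designated analyst run the 6-month comparison on coded groups, and keep by-arm results from staff who treat or telephone patients.

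**Cost.** Protocol wording only. The sponsor gives up an early efficacy claim that has about 26% power at 5 per arm. If the look is kept at p < 0.001, its power is about 1%, and final power falls only from 85.2% to 85.0%.

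### The 3-point primary endpoint in Section 12 does not match the 1.53-point difference behind the 86% power in Section 9 or the p<0.05 rule in Section 16

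*Combined protocol and SAP*

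**What the plan says.** Section 9 (Number of Subjects) takes its planning values from an earlier randomised study of intravenous dexamethasone: "mean Visual Analogue Scale for the Dexamethasone group was 2.89 (SD 1.09) compared to 3.91 (SD 2) for controls". It then argues that "an increase in effect size of at least 50% is expected with intraarterial drug administration compared to IV route", and concludes, for a two-sample t test at 0.05, that "sample size of 21 per group will provide us with 86% statistical power to detect such an effect size".

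Section 12 (Study Endpoints) opens by naming post-procedure pain, measured on a modified VAS, as the primary endpoint. It closes the same paragraph with a numerical criterion: "Our primary endpoint will be a 3-point decrease in the UFE Pain & PES score between test and controls". It gives no time point or summary measure for the comparison between arms.

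Two other places treat the primary endpoint as something that can be attained. Section 11 (Study Timelines): "Enrollment and data analysis will be conducted on a rolling basis and deemed complete upon either meeting the primary endpoints", the alternative being severe adverse events. The study design text in Section 13: "we expect that this study will reach its recruitment goal and Primary Endpoint in approximately 2 years".

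The only analysis rule is in Section 16: Student's t test for continuous variables and chi-square for categorical ones, "with significance level set at two tailed p value of <0.05". The same paragraph says: "At 6 months we will analyze the interim data for any difference in the efficacy of treatment between the groups". Section 16 does not mention 3 points.

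**The concern.** Three sections give three accounts of what the trial must show. Section 9 plans for a true difference of at least 1.53 points, Section 16 asks for a difference distinguishable from zero, and Section 12 asks for 3 points. Nothing in the text says which one decides the result or whether two must hold together.

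The region where the rules disagree is where the result is most likely to fall if the drug works as planned. A report could then call the trial positive or negative by choosing which section to cite after the data are in. Section 11 adds a second consequence, because it ties completion of the trial to the same undefined criterion.

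**Working it through.** **Inputs.** From Section 9: means 2.89 and 3.91, SDs 1.09 and 2, an uplift of 50%, 21 per arm, alpha 0.05. From Section 16: two-sided testing. From Section 12: 3 points. I take the 3 points to be on the 11-point (0–10) pain scale of Section 13.

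**1. Reproduce the 86%.**
- Reference difference: 3.91 − 2.89 = 1.02. Enlarged by half: 1.5 × 1.02 = 1.53. The protocol does not print 1.53, but it reproduces the stated power.
- Planning SD: √((1.09² + 2²)/2) = 1.611. Standardised effect: 1.53/1.611 = 0.95.
- Standard error of the difference: 1.611 × √(2/21) = 0.497.
- Two-sided power with 21 per arm: 85.2% (noncentral t), 84.6% (Welch), 86.8% (normal approximation). The stated 86% is sound for its own inputs.

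**2. Compare the sizes.** 3/1.53 = 1.96, so Section 12 asks for about twice the sizing difference. Against a control mean of 3.91 it implies a treated mean of 0.91, where the sizing implies 3.91 − 1.53 = 2.38.

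**3. Where the t test becomes significant.** The critical value on 40 degrees of freedom is 2.021, and 2.021 × 0.497 = 1.00 point. Observed differences from about 1.0 up to 3.0 pass Section 16 and fail a strict Section 12.

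**4. Reading A: 3 points is the true difference to be detected.** Power with 21 per arm exceeds 99.9%. Six per arm would give 83% and seven 89%, so 21 per arm was not derived from 3 points.

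**5. Reading B: 3 points must be observed.** For a single final analysis and a true difference d, P(observed ≥ 3) = 1 − Φ((3 − d)/0.497). The last column comes from simulation (400,000 runs per row, SDs 1.09 and 2).

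| True difference | P(observed ≥ 3) | P(p<0.05 but observed < 3) |
|---|---|---|
| 1.53 | 0.16% | 85% |
| 2.0 | 2.2% | 95% |
| 2.5 | 15.7% | 84% |
| 3.0 | 50% | 50% |

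The rows above 1.53 are included because Section 9 presents its uplift as a minimum.

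**6. If looks are repeated.** Sections 11 and 16 describe rolling analysis, but the only dated efficacy look is at 6 months. The schedules here are my assumption. At a true 1.53, the chance of reaching 3 points at some look is about 2% with looks at 10 and 21 per arm, about 7.5% at 5 and 21 (5 per arm being roughly 6 months of a 2-year accrual), and about 11% with a look after each block of 8 patients and at the end.

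Neither reading gives 86%.

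**The case against.** The best reply is that Section 12 first names a variable, post-procedure pain on a VAS. That is the kind of quantity Section 9 sizes and Section 16 would test. The 3-point sentence may then be a hoped-for or clinically relevant effect loosely called an endpoint, and on that reading the trial loses no power. This is a fair reading, but it leaves the figure unconnected to the sizing. It also sits badly with Section 11, which makes meeting the primary endpoint a ground for completion and points forward to Section 12 for its definition. The Section 13 sentence is weaker support, since it may only describe a timeline.

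The scale is also uncertain. Section 12 names the Pain & PES score, and that survey also carries 0–3 nausea and vomiting items and yes/no items. Its scoring is not in the text available to me. If the score is a composite, 3 and 1.53 are on different scales and the probabilities above cannot be computed. If the 3 points mean change from baseline, the SD would differ and so would the probabilities, but the mismatch between 3 and 1.53 would remain.

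The t-test sentence in Section 16 follows the interim-look sentence, so it could be read as applying only there. Its wording covers all data, and there is no other analysis rule.

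Finally, the missing time point is a separate and secondary gap, and the rolling-look figures depend on schedules I chose. The conclusion needs neither.

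**Conclusion.** The concern holds. The 86% is correct arithmetic for a two-sided t test of a 1.53-point difference, and it does not describe a 3-point endpoint under either reading. As a required observed difference, 3 points would be reached about 0.16% of the time at the minimum planned effect, and half the time even if the true effect were exactly 3. As a benchmark it does no harm to power, but the text does not label it so, and Section 11 gives it a deciding role. At the minimum planned effect the two success rules would give opposite answers with probability about 85%.

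The mismatch itself rests on the text alone. The probabilities assume that the reference SDs carry over, that all 42 patients contribute, and that the 3 points are on the 0–10 pain scale. This must be fixed, because it concerns the primary endpoint and its success rule.

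**What to change.** Reconcile Sections 9, 11, 12 and 16 before unblinding.

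- **Section 12:** define the primary endpoint as the between-arm difference in mean VAS pain, at one named time point or as one named summary of the scheduled post-procedure scores, tested by a two-sample t test at two-sided 0.05. State that the trial is sized for 1.53 points. Remove the 3-point figure, or label it a benchmark of clinical importance that does not decide success.
- **Section 9:** print the 1.53 and confirm that the reference means and SDs refer to the measure chosen in Section 12.
- **Section 11:** define completion by enrolment of the planned 42 patients, so that meeting the endpoint no longer triggers it. Leave the adverse-event clause as it is.
- **Section 16:** say that the 6-month look cannot declare the primary endpoint met.

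If the sponsor prefers to keep 3 points as the success criterion, Section 9 must be redone. At a true difference of 3.0 the chance of observing at least 3 is 50% whatever the sample size. With 21 per arm, an 86% chance needs a true difference of 3 + 1.080 × 0.497 = 3.54.

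The cost is a short amendment with no extra patients or data. It should be dated and documented as made without knowledge of results by arm. Planned recruitment ended in 10/2022 and the latest revision is dated 09/12/2023, so results by arm may already have been seen. If they have, the change must be disclosed as post hoc and the result reported against both criteria.
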